6.7. Continued Access to Study Intervention after the End of the Study

There will be no provision to provide continued access to study intervention after the end of the study. However, the active study intervention (sinusonic device) is available for purchase commercially.

6.8. Prior and Concomitant Therapy

Any medication or vaccine (including over-the-counter or prescription medicines, recreational drugs, vitamins, and/or herbal supplements) that the participant is receiving at the time of enrollment must be recorded along with:

- Reason for use
- Dates of administration including start and end dates
- Dosage information including dose and frequency

The medical monitor should be contacted if there are any questions regarding concomitant or prior therapy.

There are no restrictions on the concomitant medications given that the Sinusonic device is not expected to have an interaction with the study medication. However, to prevent confounding effects of a newly initiated treatment, participants will be required to be stable on their medication for at least 7 days before the start of study intervention until completion of the follow-up visit, unless, in the opinion of the investigator and sponsor, the medication will not interfere with the study.

Acetaminophen, at doses of \leq 2 grams/day, is permitted for use any time during the study. Initiation of other concomitant medications during the study period may be considered on a case-by-case basis by the investigator.

6.8.1. Rescue Medicine

The study site will not supply any rescue medication.

The use of rescue medications is allowable at any time during the study. The date and time of rescue medication administration as well as the name and dosage regimen of the rescue medication must be recorded.

6.9. Discontinuation of Study Intervention

In rare instances, it may be necessary for a participant to permanently discontinue study intervention. If study intervention is permanently discontinued, the participant should, if at all possible, remain in the study to be evaluated for 1 week. See the SoA for data to be collected at the time of discontinuation of study intervention and follow-up and for any further evaluations that need to be completed.

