2.3.3. Overall Benefit Risk Conclusion

Taking into account the measures taken to minimize risk to participants participating in this study, the potential risks identified in association with the SinuSonic device are justified by the anticipated benefits that may be afforded to participants with Sinus headache.

3. Objectives, Endpoints, and Estimands

Objectives	Endpoints
Primary	

 To determine superiority of SinuSonic intervention versus control in treatment of facial pain for patients with complaint of sinus headache that lack objective evidence of sinonasal inflammation 	
 Change in facial pain visual analogue scale at 8 weeks Change in Brief Pain Inventory Short Form at 8 weeks
Secondary	

 To determine safety of device use 	
 Number and percent of subjects reporting pain with device use Number and percent of subjects reporting epistaxis Change in Nasal Obstruction Symptom Evaluation (NOSE) Score at 8 weeks
Tertiary	

 To determine device use satisfaction 	
 Number and percent of subjects that would use the device again Number and percent of subjects that would recommend the device to others

Primary estimand

The primary clinical question of interest is:

What is the improvement in facial pain measured by facial pain VAS, and BPI-SF in patients with sinus headache treated with SinuSonic device versus a sham device regardless of discontinuation of investigational intervention for any reason and regardless of initiation of rescue medication or change in background medication.

The estimand is described by the following attributes:

- Population: Patients with complaint of sinus headache lacking objective evidence of sinonasal inflammation of nasal endoscopy or imaging
- Endpoint: change from baseline to 8 weeks in facial pain VAS, and BPI-SF
- Treatment condition:

the investigational interventions regardless of discontinuation for any reason, with or without rescue medication or change in background medication (treatment policy strategy).

- Remaining intercurrent events:

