6.10. Participant Discontinuation/Withdrawal from the Study

- A participant may withdraw from the study at any time at the participant's own request for any reason (or without providing any reason).
- A participant may be withdrawn at any time at the discretion of the investigator for safety, behavioral, or compliance reasons.
- At the time of discontinuing from the study, if possible, an early discontinuation visit should be conducted, as shown in the SoA. See SoA for data to be collected at the time of study discontinuation and follow-up and for any further evaluations that need to be completed.
- The participant will be permanently discontinued from the study intervention and the study at that time.
- If the participant withdraws consent for disclosure of future information, the sponsor may retain and continue to use any data collected before such a withdrawal of consent.
- If a participant withdraws from the study, the participant may request destruction of any samples taken and not tested, and the investigator must document this in the site study records.

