8.2. Analysis Sets

Example 1:

For the purposes of analysis, the following analysis sets are defined:

Participant Analysis Set	Description
Full analysis set (FAS)	
 • All randomized participants.
Safety analysis set (SAS)	
 • All participants who are exposed to investigational intervention.

The full analysis set will be used to analyze endpoints related to the efficacy objectives and the safety analysis set will be used to analyze the endpoints and assessments related to safety.

For the efficacy analyses, participants will be included in the analyses according to the planned investigational intervention; whereas for safety analyses, participants will be included in the analyses according to the investigational intervention they received.

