8.3.1.1. Main Analytical Approach

Statistical analysis will be conducted using SPSS version 25 (Armonk, NY: IBM Corp). Descriptive statistics such as means, range, standard deviations, frequencies, and percentages will be generated in order to present the baseline characteristics of both treatment arms. All continuous variables will be tested for normal distribution as determined by the Shapiro-Wilk test. To evaluate differences in outcome metrics between treatment arms (SinuSonic group vs sham control), paired t-tests will be used for normally distributed variables. Wilcoxon signed rank tests were used for non-normally distributed or ordinal variables. For all tests, a value of $p \leq 0.05$ will be considered statistically significant. The mean change between baseline and follow-up variables of interest will be calculated and measured against previously reported MCID thresholds when available or by using one-half of the baseline SD if not previously reported. Any missing data points will be excluded from analysis and handled similarly across all data points.

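### One week of evaluation after stopping the device, with missing values excluded, does not support the Week-8 treatment-policy estimand in all randomised participants

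*Combined protocol and SAP*

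**What the plan says.** Section 3 (primary estimand) sets the target as "Endpoint: change from baseline to 8 weeks in facial pain VAS, and BPI-SF". The treatment condition is "the investigational interventions regardless of discontinuation for any reason, with or without rescue medication or change in background medication (treatment policy strategy"), and the summary is the difference in mean changes. Section 8.2 adds: "The full analysis set will be used to analyze endpoints related to the efficacy objectives". That set is every randomised participant.

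Section 6.9 says that a participant who permanently stops the device should, where possible, "remain in the study to be evaluated for 1 week", and refers to the Schedule of Activities (SoA) for data to collect and further evaluations. Section 6.10 adds: "A participant may be withdrawn at any time at the discretion of the investigator for safety, behavioral, or compliance reasons". Participation in the study ends at that point.

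The SoA places Week 8 within +/- 3 days. It has an early-discontinuation column but no follow-up schedule after stopping. In the text available for review, that column carries no mark for VAS or BPI-SF.

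On missing data, Section 8.3.1.1 (and 8.3.1 in the same terms) states: "Any missing data points will be excluded from analysis and handled similarly across all data points".

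**The concern.** A treatment-policy estimand for discontinuation needs Week-8 outcomes from people who are no longer using the device. The plan does not secure those outcomes, and it then drops whoever lacks them. Withdrawal for compliance reasons goes further, because it ends data collection for the non-adherent participants whom this estimand must keep.

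The report could then claim an effect regardless of discontinuation when the numbers describe mainly those who kept using the device. Week-8 values that were never collected cannot be recovered at analysis.

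**Working it through.** **Day count.** Week 8 is Day 56 and its window opens on Day 56 - 3 = 53. One further week reaches the window only if the device is stopped on Day 53 - 7 = 46 or later, and reaches Day 56 itself only from Day 49. A stop at the end of Weeks 1 to 6 ends evaluation on Days 14 to 49, before the window opens.

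**The plan's own figure.** The documents give no discontinuation rate and no dropout allowance. The one related figure is in Section 8.4: over 90% power with 60 participants and response of 30% against 70%. At 30 per arm, the unpooled normal approximation gives 92.2% and the pooled form 89.3%, so the claim is reproduced in substance. Under the pooled form, losing 10% of each arm (27 left) gives 85.7%, and losing 20% (24 left) gives 81.2%.

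**Bias on the VAS: inputs.**
- Active completers improve 25 mm. This is the open-label 4-week change, 59.6 - 34.6 = 25.0.
- Sham completers improve 13 mm (assumed).
- Stoppers improve 5 mm in either arm (assumed).
- The stopping rate d in each arm is assumed and varied.

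Treatment-policy mean per arm = (1 - d) x completer change + d x stopper change. If no stopper has a Week-8 value, complete-case analysis shows 25 - 13 = 12.0 mm in every row.

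| Stopping, active / sham | Active mean (mm) | Sham mean (mm) | Treatment-policy difference (mm) | Complete-case error |
|---|---|---|---|---|
| 5% / 5% | 24.0 | 12.6 | 11.4 | +5% |
| 10% / 10% | 23.0 | 12.2 | 10.8 | +11% |
| 20% / 20% | 21.0 | 11.4 | 9.6 | +25% |
| 10% / 5% | 23.0 | 12.6 | 10.4 | +15% |
| 20% / 5% | 21.0 | 12.6 | 8.4 | +43% |
| 5% / 20% | 24.0 | 11.4 | 12.6 | -5% |

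With equal stopping rates and the same stopper change in both arms, the treatment-policy difference is (1 - d) times the completer difference. The overstatement is then d/(1 - d), whatever the mm values.

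**Some stoppers observed.** If stopping times are uniform over 56 days and one week of evaluation follows, m = 49/56 = 87.5% of stoppers lack Week-8 data. The complete-case mean per arm is [(1 - d) x C + d(1 - m) x 5] / [(1 - d) + d(1 - m)], where C is the completer change.
- 5% / 5%: 11.92 against 11.4 mm, an overstatement of 4.6%.
- 20% / 20%: 11.64 against 9.6 mm, 21%.
- 20% / 5%: 11.45 against 8.4 mm, 36%.

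Counting from Day 46 instead (m = 46/56 = 0.82), these become 4.3%, 20% and 34%.

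**Sensitivity to the stopper value**, at 20% / 5% with no stopper observed:
- 5 mm: 8.4 mm, 43%.
- 15 mm: 23.0 - 13.1 = 9.9 mm, 21%.
- 25 mm: 25.0 - 13.6 = 11.4 mm, 5%.

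**Participants lost** if no stopper has Week-8 data: 30 x (active rate + sham rate), which is 3 of 60 at 5% per arm, 6 at 10% and 12 at 20%.

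**The case against.** The strongest reply is that Section 6.9 does not limit evaluation to one week. It can be read as a minimum, with the SoA governing the rest. Section 4.1 schedules VAS and BPI-SF through Week 8 with no exception for people off the device, and Section 7 makes adherence to the SoA mandatory. This reading is possible, but no sentence states it. The SoA shows no follow-up after stopping. Section 7.3.6.2 does extend follow-up to people who discontinue, but only for device deficiencies. If continued collection was intended, one sentence would settle it.

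The SoA evidence is weaker than it first looks. The six VAS marks match the six times in Section 4.1 in number. However, the first falls under screening and not baseline, and the satisfaction questionnaire's only mark sits under early discontinuation, although satisfaction is compared at 8 weeks. The table may have shifted in extraction and should be checked against the original. The point does not depend on it.

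Size is the better objection. Section 6.9 says: "In rare instances, it may be necessary for a participant to permanently discontinue study intervention". In the open-label study, 86% would use the device again and no major adverse events occurred. At 5% stopping per arm the illustrated bias is 0.6 mm. If the SD is the pilot's follow-up value of 21.7 mm, the standard error of the difference is 21.7 x sqrt(2/30) = 5.6 mm, so the bias is about a tenth of a standard error. The larger figures need unequal stopping and little improvement among stoppers, and rescue use could raise that improvement. All of this stands as a limit on size. It does not remove the mismatch.

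Section 8.3.2 defers further detail to an SAP, and no separate SAP text is available. An SAP could add sensitivity analyses, but it could not supply uncollected values.

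**Conclusion.** The concern holds. As written, Sections 6.9, 6.10 and 8.3.1 do not deliver the estimand in Section 3 for device discontinuation. Week-8 data are not secured for anyone stopping before about Day 46, and the exclusion rule leaves something close to a completers comparison.

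The true bias is unknown. Under the assumptions shown, with no stopper observed, it runs from a 5% understatement to a 43% overstatement. It is small if stopping is rare and balanced. Differential stopping by arm is an assumption, and the direction depends on which arm stops more.

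The rescue and background medication part of the estimand is not affected. Section 6.8.1 says: "The use of rescue medications is allowable at any time during the study", and such use does not end follow-up.

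This must be fixed before data collection, because it concerns the primary endpoint, enrolment is capped at 60 with no dropout allowance, and the loss is irreversible.

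**What to change.** 1. In Sections 6.9 and 6.10 and in the SoA, state that the remote VAS and BPI-SF questionnaires continue at every scheduled time through Week 8 for anyone who stops or under-uses the device but has not withdrawn consent. This concerns data collection only.
2. Add VAS and BPI-SF at early discontinuation for those leaving the study altogether.
3. In Sections 8.3.1 and 8.3.1.1, replace exclusion of missing values with an analysis that uses all post-baseline data from all randomised participants under a stated missing-data assumption. A repeated-measures mixed model is one option, but without data collected after stopping it would not by itself target treatment policy. Item 1 therefore comes first.
4. Add a sensitivity analysis that assumes no benefit after stopping.
5. Separately, reconcile the 4-week questionnaire schedule in the Synopsis and the 4-week completion definition in Section 4.4 with the Week-8 endpoint in Sections 3, 4.1 and 8.1 and in the SoA. Check the satisfaction questionnaire's mark against the original SoA table.

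The cost is wording edits, a few more remote questionnaires for people who stop early, no clinic visits, and slightly more analysis work.

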6.10. Participant Discontinuation/Withdrawal from the Study

- A participant may withdraw from the study at any time at the participant's own request for any reason (or without providing any reason).
- A participant may be withdrawn at any time at the discretion of the investigator for safety, behavioral, or compliance reasons.
- At the time of discontinuing from the study, if possible, an early discontinuation visit should be conducted, as shown in the SoA. See SoA for data to be collected at the time of study discontinuation and follow-up and for any further evaluations that need to be completed.
- The participant will be permanently discontinued from the study intervention and the study at that time.
- If the participant withdraws consent for disclosure of future information, the sponsor may retain and continue to use any data collected before such a withdrawal of consent.
- If a participant withdraws from the study, the participant may request destruction of any samples taken and not tested, and the investigator must document this in the site study records.

6.11. Lost to Follow up

A participant will be considered lost to follow-up if the participant repeatedly fails to return for scheduled visits and is unable to be contacted by the study site.

The following actions must be taken if a participant fails to return to the clinic for a required study visit:

- The site must attempt to contact the participant and reschedule the missed visit as soon as possible, counsel the participant on the importance of maintaining the assigned visit schedule and ascertain whether the participant wishes to and/or should continue in the study.
- Before a participant is deemed lost to follow-up, the investigator or designee must make every effort to regain contact with the participant (where possible, 3 telephone calls, and if necessary, a certified letter to the participant's last known mailing address or local equivalent methods). These contact attempts should be documented in the participant's medical record.
- Should the participant continue to be unreachable, the participant will be considered to have withdrawn from the study.

- Site personnel, or an independent third party, will attempt to collect the vital status of the participant within legal and ethical boundaries for all participants randomized, including those who did not get study intervention. Public sources may be searched for vital status information. If vital status is determined as deceased, this will be documented and the participant will not be considered lost to follow-up. Sponsor personnel will not be involved in any attempts to collect vital status information.

7. Study Assessments and Procedures

- Study procedures and their timing are summarized in the SoA. Protocol waivers or exemptions are not allowed.
- Adherence to the study design requirements, including those specified in the SoA, is essential and required for study conduct.
- All screening evaluations must be completed and reviewed to confirm that potential participants meet all eligibility criteria. The investigator will maintain a screening log to record details of all participants screened and to confirm eligibility or record reasons for screening failure, as applicable.
- Procedures conducted as part of the participant's routine clinical management [(eg, blood count, ENT examination)] and obtained before signing of the ICF may be utilized for screening or baseline purposes provided the procedures met the protocol-specified criteria and were performed within the timeframe defined in the SoA.
- In the event of a significant study-continuity issue (eg, caused by a pandemic), alternate strategies for participant visits, assessments, medication distribution and monitoring may be implemented by the sponsor or the investigator, as per local health authority/ethics requirements.
- Safety/laboratory/analyte results that could unblind the study will not be reported to investigative sites or other blinded personnel until the study has been unblinded.

7.1. Efficacy and/or Immunogenicity Assessments

Study outcomes will be assessed using the facial pain visual analogue scale (VAS)⁵, and Brief Pain Inventory-Short Form (BPI-SF)^{13,14}. The facial pain VAS score is a scale from 0-100 millimeters (mm) and asks patients to rate the severity of their facial pain over a previous one week recall period with higher scores indicating greater pain intensity. Additionally, a current VAS pain score and an immediate 5-minute post-use current VAS pain score will be assessed. A prior study looking at orofacial pain reported a minimal clinically important difference (MCID) of 1.2 for VAS pain. The BPI-SF assesses pain at its “worst”, “least”, “mean”, and “now” (current pain). In clinical trials, the items “worst” and “mean” have been each used singly to represent the pain severity. Worst and mean pain will be assessed over a previous one week recall period. BPI-SF also measures how much pain interferes (BPI interference) with seven daily activities including general activity, walking, work, mood, enjoyment of life, relations with others, and sleep. BPI pain interference is typically scored as the mean of the seven interference items. All items are rated on a 0-10 scale with 0 representing no pain/no interference and 10 representing pain as bad as you can imagine/interferes completely. A distribution-based approach using one-half the SD will be used to determine MCID values for BPI-SF, as there is a paucity of research assessing the MCIDs for these pain measures for facial pain/headache. Planned timepoints for all efficacy assessments are provided in the SoA.

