Just as efficacy for triptans was first demonstrated and popularized in the primary headache literature before utilization in sinus headache studies, medical devices are following a similar trend with the recent advent of transcutaneous stimulation devices.⁹ Recently, two studies investigating use of acoustic vibration with oscillating expiratory pressure applied to the nasal cavity for treatment of nasal congestion were performed looking at cohorts of patients with complaint of congestion.^{10,11} One study demonstrated a significant improvement in objective measures of nasal obstruction and both demonstrated improvements in subjective measures of obstruction. Of note, in both studies, investigators noted improvements in facial pain/pressure. We recently conducted an open label trial to determine if simultaneous administration of acoustic vibration and oscillating expiratory pressure (using Sinusonic device) affects the severity of facial pain among patients with complaint of sinus headache. Twenty-nine patients (mean age 49 years, 55% female) completed our preliminary study without any major adverse events. At the 4-week follow-up, facial pain visual analog scale (VAS)⁵ improved from mean standard deviation(SD) of 59.6+/-15.7 to 34.6+/-21.7($p<0.001$) and approximately 70% of patients achieving a minimal clinically important difference (MCID) across all pain metrics. Eighty-six percent of subjects would use device again and recommend it to others. As the next step, we propose a randomized controlled trial. Preliminary data demonstrates that the device is low-risk, with high patient satisfaction, and patients are able to perform the intervention at home with ease.

Table 1: Objectives and Endpoints

Objectives	Endpoints
Primary	
 To assess relative improvements in facial pain/pressure after 8-weeks of twice daily use of the SinuSonic device compare to a sham device
	
 Facial pain visual analogue scale (0-10) (1-week recall period) Facial pain visual analogue scale (0-10) (immediate 5-minute post use recall) Brief Pain Inventory-Short Form
Secondary	
 Safety data Device use satisfaction Nasal obstruction

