	
 Percent achieving a minimal clinically important difference Adverse events reported via questionnaire (pain, epistaxis, etc.) Percentage willing to use again and recommend device to others Nasal obstruction symptom evaluation (NOSE) Score change

Overall Design:

This is a parallel, placebo-controlled multicenter randomized trial. The study population will consist of healthy volunteers with sinus headache/pain lacking objective evidence of chronic sinusitis. This will be a single-blinded study blinded to the participants. Because this study will involve minimal intervention from the investigators (i.e. participants will fill out surveys remotely), there will be minimal influence from the investigators and analysts end. Participants will be randomized to the treatment or the sham-placebo arm and the device they received (either device or sham), will be recorded in a secure database. Following screening, investigational intervention assignment will be performed by randomization in a 1:1, investigational device: sham ratio. Data will be collected and stored in an electronic data storage system.

Brief Summary:

The purpose of this study is to measure facial pain/pressure with a novel device using acoustic vibrations with oscillating expiratory pressure compared with a sham device in participants with sinus pain/headache lacking objective evidence of sinonasal inflammation.

Study details include:

- The study duration will be up to 12 months.
- The treatment duration will be up to 8 weeks.

- The visit frequency will be 0 visits. Participants will fill out questionnaires fielded via an electronic data capture system at 1 week, 2 weeks, 3 weeks, and 4 weeks of device use.

[figure not shown]
Number of Participants:

Approximately 120 participants will be screened to achieve 60 enrolled.

A maximum of 60 participants will be enrolled

Study Arms and Duration:

The total duration of study participation with screening, run-in (i.e., delivery of device), and device use is 11 weeks. Participants will use the investigational or sham device for 2 minutes, twice-daily for the entire 8-week study duration.

Data Monitoring/Other Committee:**1.2. Schema**

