1.3. Schedule of Activities (SoA)

Procedure	Screening (up to 3 weeks before Day 1)	Baseline (up to 3 weeks before Day 1)	Intervention Period (8 weeks)					E/D	Notes E/D = Early Discontinuation
			Day 1 +/- 3 Days	Week 2 +/- 3 Days	Week 4 +/- 3 Days	Week 6 +/- 3 Days	Week 8 +/- 3 Days		
Informed consent	X								
Inclusion and exclusion criteria	X								Recheck clinical status before randomization and/or first dose of investigational intervention.
Demographics	X								
Medical history (includes substance use)	X								Substances: drugs, alcohol, tobacco, and caffeine
Current medical conditions	X								
Randomization		X							
Study intervention			X	X	X	X	X		

Procedure	Screening (up to 3 weeks before Day 1)	Baseline (up to 3 weeks before Day 1)	Intervention Period (8 weeks)					E/D	Notes E/D = Early Discontinuation
			Day 1 +/- 3 Days	Week 2 +/- 3 Days	Week 4 +/- 3 Days	Week 6 +/- 3 Days	Week 8 +/- 3 Days		
AE review				←=====→					
SAE review: Including solicited administration-site events if applicable: pain or bleeding				←=====→				X	Pain Epistaxis
Device deficiencies			←=====→					X	
Concomitant medication review		X							

Procedure	Screening (up to 3 weeks before Day 1)	Baseline (up to 3 weeks before Day 1)	Intervention Period (8 weeks)					E/D	Notes E/D = Early Discontinuation
			Day 1 +/- 3 Days	Week 2 +/- 3 Days	Week 4 +/- 3 Days	Week 6 +/- 3 Days	Week 8 +/- 3 Days		
Efficacy questionnaire assessment: • VAS facial pain (1 week recall)	X		X	X	X	X	X		
Efficacy questionnaire assessment: • BPI-SF		X	X	X	X	X	X		
NOSE		X					X		
Device use satisfaction questionnaire								X	

2. Introduction

Sinusonic is an FDA registered novel medical device employing simultaneous acoustic vibrations and positive expiratory pressure to the nasal cavity that has been studied for management of nasal congestion and, more recently, sinus headache.

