Just as efficacy for triptans was first demonstrated and popularized in the primary headache literature before utilization in sinus headache studies, medical devices are following a similar trend with the recent advent of transcutaneous stimulation devices.⁹ Recently, two studies investigating use of acoustic vibration with oscillating expiratory pressure applied to the nasal cavity for treatment of nasal congestion were performed looking at cohorts of patients with complaint of congestion.^{10,11} One study demonstrated a significant improvement in objective measures of nasal obstruction and both demonstrated improvements in subjective measures of obstruction. Of note, in both studies, investigators noted improvements in facial pain/pressure.

We recently conducted an open label trial to determine if simultaneous administration of acoustic vibration and oscillating expiratory pressure (using Sinusonic device) affects the severity of facial pain among patients with complaint of sinus headache. Twenty-nine patients (mean age 49 years, 55% female) completed our preliminary study without any major adverse events. At 4-weeks follow-up, facial pain visual analog scale (VAS) improved from mean standard deviation(SD) of 59.6+/-15.7 to 34.6+/-21.7(p<0.001) and approximately 70% of patients achieving a minimal clinically important difference (MCID) across all metrics. Eighty-six percent of subjects would use device again and recommend it to others. As the next step, we propose a randomized controlled trial. Preliminary data demonstrates that the device is low-risk, with high patient satisfaction, and patients are able to perform the intervention at home with ease.

In regards to device use, the device comes with a clear plastic tab at the base of the device. This tab must be removed prior to device use. For a full session, there is a trigger that must be held down after which

subjects should breathe in and out through their nose with a normal amount of force and speed. A gentle humming will be felt and heard and during exhalations, a fluttering sound will be appreciated. After a full session of use (2 minutes), the device will go into a rest mode for 6 minutes.

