5.1. Inclusion Criteria

Participants are eligible to be included in the study only if all of the following criteria apply:

1. Participant must be ≥ 18 years of age inclusive, at the time of signing the informed consent.
2. Participants who are overtly healthy as determined by medical evaluation including medical history and physical examination.
3. Capable of giving signed informed consent
4. Facial pain or pressure for ≥ 3 months of symptom duration
5. Pain/pressure VAS score of ≥ 5
6. Lund MacKay Score of ≤ 3 with no single sinus score of 2

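### The facial pain VAS runs 0-10 in the Synopsis but 0-100 mm in Section 7.1, and its MCID (1.2) and entry threshold (≥ 5) carry no units

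*Combined protocol and SAP*

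**What the plan says.** The facial pain VAS is a primary endpoint; Section 3 lists it as "Change in facial pain visual analogue scale at 8 weeks" and gives no range. The range and the thresholds appear elsewhere:

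- **Synopsis, Objectives and Endpoints table:** "Facial pain visual analogue scale (0-10) (1-week recall period". The five-minute post-use item is also given as 0-10. The same table lists the secondary outcome "Percent achieving a minimal clinically important difference", which the Section 3 endpoint list does not contain.
- **Section 7.1:** "The facial pain VAS score is a scale from 0-100 millimeters (mm", again with one-week recall. Current-pain and post-use VAS items are added without a range. The VAS MCID is given as 1.2, taken from an orofacial pain study, without a unit.
- **Section 5.1, criterion 5:** "Pain/pressure VAS score of ≥ 5", with no unit and no recall period.
- **Section 1.3, Schedule of Activities:** the only VAS row, marked at Screening among other times, is "VAS facial pain (1 week recall", with no range.
- **Section 2, pilot data:** "facial pain visual analog scale (VAS) improved from mean standard deviation(SD) of 59.6+/-15.7 to 34.6+/-21.7".
- **Sections 8.3.1 and 8.3.1.1:** mean change is to be compared with published MCIDs where they exist, and otherwise with half the baseline SD.

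No section converts between the two ranges or says which one the 1.2 and the 5 belong to.

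**The concern.** One item has two stated ranges, and the two thresholds that depend on the range have no units. Three uses are exposed: the only pain-severity criterion for entry, the percentage reaching the MCID, and the comparison of mean change with the MCID. If the thresholds are meant on 0-10 but are applied to the instrument as Section 7.1 defines it, each is a tenth of its intended size. The MCID outcome would then count almost any improvement as clinically important, and the entry criterion would hardly select for severity.

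**Working it through.** **1. The two ranges.** The Synopsis table and Section 7.1 both describe the one-week-recall item, one as 0-10 and the other as 0-100 mm. The pilot means of 59.6 and 34.6 are possible only on 0-100. The later statement in Section 7.1 that items are rated 0-10 follows the BPI-SF description and does not settle the VAS. For the post-use item there is a range in the Synopsis and none in Section 7.1. For the current-pain item there is none in either place.

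**2. Size of the ambiguity.**

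| Threshold | On 0-10 | On 0-100 mm |
|---|---|---|
| MCID 1.2 | 1.2/10 = 12% of range | 1.2/100 = 1.2% of range |
| Entry ≥ 5 | 5/10 = 50% of range | 5/100 = 5% of range |

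Against the pilot baseline SD, 1.2 mm is 1.2/15.7 = 0.08 SD and 12 mm is 12/15.7 = 0.76 SD. For comparison, the plan's fallback MCID is 0.5 SD.

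**3. Effect on the MCID responder percentage (illustration).** Inputs are the pilot SDs of 15.7 and 21.7. Assumptions: changes are normal and the baseline-to-follow-up correlation r is 0.5, with a range of 0.3 to 0.7. The documents do not give r.

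SD of change = √(15.7² + 21.7² − 2r × 15.7 × 21.7). At r = 0.5 this is √(246.49 + 470.89 − 340.69) = √376.69 = 19.41 mm. At r = 0.3 it is 22.65 mm and at r = 0.7 it is 15.51 mm.

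Share reaching threshold c with mean improvement m = 1 − Φ((c − m)/SD):

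| Mean improvement | c = 1.2 mm | c = 12 mm |
|---|---|---|
| 0 mm, r = 0.5 | 1 − Φ(0.062) = 47.5% | 1 − Φ(0.618) = 26.8% |
| 0 mm, r = 0.3 / 0.7 | 47.9% / 46.9% | 29.8% / 21.9% |
| 25 mm (59.6 − 34.6), r = 0.5 | 89.0% | 74.9% |
| 25 mm, r = 0.3 / 0.7 | 85.3% / 93.8% | 71.7% / 79.9% |

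Under this model half of a group with zero mean change improves by some amount. A 1.2 mm threshold is therefore close to counting everyone who improves at all.

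**4. Effect on entry.** A score of 5 mm lies (59.6 − 5)/15.7 = 3.5 SD below the pilot baseline mean, so in a similar population it would exclude very few. The pilot's own entry criteria are not given, so its baseline may already be selected, and the number of patients whose eligibility turns on the reading cannot be estimated.

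**5. Stated power.** Section 8.4 claims over 90% for 30% versus 70% response with 60 participants, 30 per arm. The unpooled normal approximation gives Φ(0.4/√(2 × 0.21/30) − 1.96) = Φ(1.42) = 92.2%. The pooled version gives Φ((0.4 − 1.96√(2 × 0.25/30))/√(2 × 0.21/30)) = Φ(1.24) = 89.3%. Both are within about two points of the claim, and no VAS unit enters the calculation.

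**The case against.** The best defence is that there is no real conflict: 0-10 in cm and 0-100 in mm describe the same line, and 1.2 and 5 sit naturally on 0-10. The Synopsis range comes before criterion 5, and Section 7.1 attributes the 1.2 to another study without placing it on the mm scale. This largely stands. The combination of 1.2 mm and 5 mm is one possible reading, not the literal text, and the 0-10 reading is plausible. It does not remove the need for a unit, because the section that defines the instrument gives only mm and sets 1.2 beside it.

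Several stronger readings are tempting but not supported:

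- **The pilot settles the scale of the MCID.** The pilot reported "approximately 70% of patients achieving a minimal clinically important difference (MCID) across all metrics". With a 25 mm mean change, the model needs a threshold of 25 − 0.524 × 19.41 = 14.8 mm to give 70%, nearer 12 than 1.2. But the percentage is not stated for VAS alone. If it were 20 of 29 (69%), the exact 95% interval would be 49-85%, and at r = 0 a 1.2 mm threshold gives 81%, which lies inside it.
- **The responder outcome could not separate the arms.** At r = 0.5, the gap between zero and 25 mm mean change is 89.0 − 47.5 = 41.5 points at 1.2 mm and 74.9 − 26.8 = 48.1 points at 12 mm. What is lost is mainly the meaning of the outcome as clinically important improvement.
- **The primary test or the power is undermined.** Rescaling leaves a test of mean change unchanged if one scale is used throughout. Section 8.4 does not define response. If it means reaching the VAS MCID, the ambiguity touches that definition but not the stated power arithmetic.
- **Sites or time points will mix scales.** The electronic questionnaire is not in the documents, so this cannot be shown.
- **Criterion 5 certainly uses the one-week item.** The schedule's single VAS row suggests it, but the criterion names no recall period.

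**Conclusion.** The point holds as a defect of definition and should be fixed. The discrepancy in range and the missing units are certain from the text. Each threshold is ambiguous by a factor of ten. Applied to the 0-100 mm instrument, 1.2 would make the MCID percentage nearly uninformative about clinically important change: about 47% (47-48%) responders with no mean change, against about 27% (22-30%) at 12 mm. These figures assume normal changes, the pilot SDs and r between 0.3 and 0.7, and they illustrate one reading without forecasting the trial. Mean change would also be judged against a threshold a tenth of the 0-10 value. The entry threshold would select little on severity under the mm reading, but the effect on eligibility cannot be sized from the documents.

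**What to change.** State one VAS scale, with units, in the Synopsis table, Section 5.1, Section 7.1 and the electronic questionnaire, covering the one-week-recall, current-pain and post-use items. Check the source of the 1.2 MCID and write it with units on the chosen scale: 12 mm if the source used 0-10 and 0-100 mm is kept. The sponsor must reconcile criterion 5 in Section 5.1 with the chosen scale and name the VAS item it refers to; no cut-off is proposed here. The cost is wording changes and a check of the questionnaire, with no additional participants and no change to the primary test.
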